## 6.0 Inclusion and Exclusion Criteria

### 6.1 Screening Process

Participant eligibility will be determined using a screening questionnaire, by the research coordinator. Prior to administering the eligibility questions, all potential participants will be notified that there are specific inclusion criteria for the study, and not everyone will qualify for the study. Potential participants will be notified after the end of the screening questionnaire whether they are eligible or ineligible based on their responses. In some cases, it is possible that eligibility may not be readily apparent. In those cases, potential participants will be informed that their responses will be reviewed by the study PI, and they will be followed up in the next few days.

### 6.2 Inclusion and Exclusion Criteria

Inclusion:

- Aged 21 or older
- Current tobacco smoker, defined as having smoked daily over the past 7 days
- Willing to make a serious quit attempt in the next 30 days ("Yes" to "In the next 30 days, are you willing to try quitting smoking for at least 24 hours?")
- Considered food insecure, based on past 30-day screening using the 2-item Hunger Vital Sign, or by virtue of having visited a food pantry in the past 30 days
- A reliable telephone number and a local mailing address where participant can be reached during the duration of the study

Exclusion:

- Aged 20 or younger
- Non-smoker, or a current tobacco smoker who did not smoke daily over the past 7 days
- Not interested in quitting at this time, assessed by unwillingness to make a serious quit attempt in the next 30 days ("No" to "In the next 30 days, are you willing to try quitting smoking for at least 24 hours?")
- Did not recently experience food insecurity, based on past 30-day screening using the 2-item Hunger Vital Sign, or has not visited a food pantry in the past 30 days
- Does not have a reliable telephone number and a local mailing address where participant can be reached during the duration of the study

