## 1.0 Objectives

Tobacco use continues to be a leading cause of preventable disease and early death. The majority of people who smoke are interested in quitting and attempt to quit each year, but successfully quitting can be challenging for many reasons. In particular, smoking cessation can be especially hard when smokers are dealing with unmet social and health needs and areas of financial stress, which are disproportionately experienced by low-income smokers. In this study, we extend previous research showing that food insecurity is independently associated with higher odds of smoking and can act as a barrier to quitting smoking. Therefore, we design and test a 12-week intervention to assist food-insecure smokers who are ready and willing to make a quit attempt. Beyond providing the quit assistance that smokers normally receive, the research seeks to address food insecurity in the short-term by providing economic food assistance during the quit attempt that will help to meet food needs. We will adapt a patient navigation model in which a designated study navigator can help bridge resources and referrals related to tobacco cessation and food access, and provide economic food assistance based on individualized needs. We will recruit 60 participants for a 12-week study, and all participants will be smokers who are ready to quit and have recently experienced food insecurity. All participants will receive quit assistance and information on local food assistance resources, and a monthly check-in from the navigator. In addition, half of the participants (n=30) will be randomly assigned to the intervention arm, and will receive economic food assistance to partially meet their food needs and reduce food insecurity during the cessation attempt. We will assess feasibility and acceptability of the intervention, and preliminary outcomes related to smoking cessation, such as the number of quit attempts lasting 24 hours or more and the longest length of abstinence from tobacco. By conducting this study, we seek to understand whether this type of intervention is feasible to conduct, and acceptable to those who participate. The study findings will serve as the basis of future research on understanding and addressing tobacco-related and food insecurity-related health disparities. Our main research question is whether addressing food insecurity specifically during a smoking cessation attempt is helpful for increasing quitting success rates.

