**RANDOMIZATION, ALLOCATION:** After the baseline telephone (or online) survey is completed, participants will be randomized in the Intervention arm or the Control arm with a 50/50 chance to be randomized in either arm. The study analyst who has no contact with participants will use a computer-generated random number table to assign participants. In either arm, in Week 1 of the study, all participants will be connected to receive usual care for tobacco cessation, based on their preferences. In either arm, the study navigator (a community health worker) will review participant responses from the baseline telephone survey and reach out to all participants by telephone. This conversation may involve referrals to the tobacco quitline, referrals to counseling/classes offered at MetroHealth or in the community (such as Freedom from Smoking classes), nicotine replacement therapy and/or pharmacotherapy as prescribed by their primary care provider. The study navigator will provide linkages and information to the services available to the participant, which will be documented in a semi-structured call log, and used as the basis of following up on use of tobacco cessation services in subsequent telephone check-ins in Week 4 and Week 8.

In either arm, participants also receive information from the study navigator about local food assistance resources available to them, such as a list of food pantries and community meal sites and eligibility information about federal food assistance programs. Provision of this information will also be documented by a semi-structured call log, and will be used as the basis of following up on food assistance resources in subsequent check-ins in Week 4 and Week 8. Information about tobacco cessation and food assistance resources are provided by telephone and/or in writing, which is within the scope of work for a community health worker.

In the Intervention arm only, participants will receive economic food assistance to meet their individual food and grocery needs during the cessation attempt/study period. This is provided on a monthly basis (3 times during the 12 weeks of the study) during Week 1, Week 5, and Week 9.

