Participants in the Intervention arm will be provided \$83 per month (for a total of \$250 for the 12 weeks) to partially support the cost of food (i.e., provide short-term food insecurity relief) during the cessation attempt. These funds will be in the form of VISA gift cards, a check, a direct deposit transaction, or a Zelle transaction, depending on the participant's choosing. The check, direct deposit, and Zelle options are processed through PNC Bank's E-payment system. We are NOT collecting any bank information from the participants. The participant will confirm their bank account information with PNC to deposit the funds or mail the check, but the researchers will not see that information.

**Follow-ups:** About 4 weeks after randomization, the study navigator will conduct a general check-in call with all participants by telephone to follow-up on referrals provided and additional referrals needed. The length of the call is anticipated to be 15 minutes. The content/topics and length of discussions will be documented through call logs.

About 8 weeks after randomization, the study navigator will conduct a general check-in call with all participants by telephone to follow-up on referrals provided and additional referrals needed. The length of the call is anticipated to be 15 minutes. The content/topics and length of discussions will be documented through call logs.

Twelve weeks after randomization (end-of-study), the study coordinator will contact participants to complete the follow-up telephone or online REDCap survey, which is expected to last 30-45 minutes.

**END-OF-STUDY QUALITATIVE INTERVIEWS:** Participants who were randomized to the intervention group and have completed the protocol will be invited to participate in an end-of-study qualitative interview to provide more context about food access, and to share their experiences with the intervention.

**Recruitment:** Similar to the recruitment procedures for the overall study, we will first mail an invitation letter to prior participants, who can contact the research team if they are interested and willing to discuss their food access and study intervention experiences through a telephone interview. As needed, we will follow up with a telephone call to the target subsample of participants who were sent invitation letters.

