### 7.3 Methods Used to Identify Potential Participants

We will use the electronic health record (EHR) to prescreen potential participants for this study. Potential participants will comprise of current MetroHealth patients from a total of 7 MetroHealth sites within Cuyahoga county. We will use the EHR to prescreen for age (21 years or older), smoking status as documented in the EHR (documented as currently smoking), and food insecurity status (documented as food insecure based on social determinants of health screening conducted during the most recent visit). Using this list, we will send out a recruitment packet in the mail, consisting of a 1-page study flyer with key information and a copy of the informed consent document, in the form of a non-return cover memo. The flyer will instruct potential participants to contact the study team by telephone for further information about the study, and to see if they qualify.

As needed and based on recruitment rate, the research team will also make telephone calls to follow-up with potential participants, after having sent recruitment letters (i.e., there is no “cold” calling without sending letters beforehand). Using the prescreened list of individuals, we will randomly follow up with individuals on the list until we reach the enrollment target for the wave (n=15-20 enrolled in each wave; 3-4 enrollment waves; 60 participants in total will be recruited for this study).

To identify potential participants for the end-of-study qualitative interviews, we will attempt to contact everyone who would be eligible based on their intervention assignment and completion of the protocol.

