## 11.0 Data Analysis Plan

As a pilot study, the primary outcomes pertain to the assessment of feasibility and acceptability, and to derive preliminary estimates of tobacco cessation measures and food security status. We will conduct t-tests and chi-square tests to explore group differences. Feasibility will be assessed by examining the number of participants screened, percent eligible to participate, refusal rate, and attrition rate between baseline and 12-week follow-up. We will examine participants' utilization of resources related to tobacco cessation and food assistance, to examine feasibility of the navigation model. We will gain feedback from the navigator regarding the process of providing referrals and individualized food assistance. We will evaluate acceptability through open-ended questions to elicit participant feedback regarding their perceptions of helpfulness of food assistance in meeting food needs, helpfulness of food assistance specifically during cessation attempt, and additional barriers and facilitators to making a quit attempt or staying quit.

Qualitative interviews will be transcribed and analyzed using inductive and deductive coding process.

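### The inclusion and exclusion bullets disagree on people who qualify by a pantry visit alone; if they are admitted, the unadjusted food security comparison may be weakened

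*Combined protocol and SAP*

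**What the plan says.** Section 6.2 gives two routes to the food-insecurity criterion: "Considered food insecure, based on past 30-day screening using the 2-item Hunger Vital Sign, or by virtue of having visited a food pantry"; a visit counts if it fell within the last 30 days. The mirror exclusion in the same section removes anyone who "Did not recently experience food insecurity, based on past 30-day screening using the 2-item Hunger Vital Sign, or has not visited a food pantry", again over a 30-day window.

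Upstream, Section 7.3 limits the mailing list to patients "documented as food insecure based on social determinants of health screening conducted during the most recent visit". It does not say how recent that visit must be.

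The funds are meant "to partially support the cost of food (i.e., provide short-term food insecurity relief) during the cessation attempt" (Section 5.2). Section 11.0 includes among the pilot's aims "to derive preliminary estimates of tobacco cessation measures and food security status", with t-tests and chi-square tests to explore differences between arms. It names no food-security instrument, scoring or recall period, and uses neither the baseline level nor the entry route. Section 3.0 does not list food security among the endpoints. Randomisation is "with a 50/50 chance to be randomized in either arm" (Section 5.2), with no stratification described.

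**The concern.** The trial rests on a chain: funds lower food insecurity, and lower food insecurity helps quitting. The week-12 comparison of food security is the only quantitative between-arm check on the first link.

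Two features could blur it. First, if a pantry visit alone is enough, some participants may screen food secure at entry and have little room to improve. Second, those who enter on a positive screen all start insecure, and funds that cover only part of food costs may move them within insecurity rather than out of it. A yes/no status, if that is what is compared, would miss such movement.

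A null or small difference would then be hard to read: it could mean that the funds did little, or that the comparison was a poor detector. Section 1.0 says the findings will be a basis for later research, so the ambiguity would carry forward.

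**Working it through.** **Step 1: the two bullets side by side (Section 6.2).** Each combination of Hunger Vital Sign (HVS) result and pantry visit in the past 30 days:

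| HVS | Pantry visit | Inclusion bullet | Exclusion bullet, read literally | Exclusion bullet, read as neither |
|---|---|---|---|---|
| positive | yes | admits | does not bar | does not bar |
| positive | no | admits | bars | does not bar |
| negative | yes | admits | bars | does not bar |
| negative | no | does not admit | bars | bars |

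Read literally, the bullets conflict in two of the four rows. They agree only if the exclusion means neither a positive screen nor a pantry visit. The rest of the check concerns the third row, and applies only if such people are admitted.

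**Step 2: inputs.** From Section 1.0: "We will recruit 60 participants for a 12-week study" and "half of the participants (n=30) will be randomly assigned to the intervention arm", so 60/2 = 30 per arm. The documents give no alpha, power, effect size or pantry-only share, so there is no power figure to reproduce. Assumptions, for illustration only:

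- q, the share who enter by pantry visit with a negative screen: 10%, 20%, 30%.
- Food insecurity at week 12 among HVS-positive entrants: 80% control, 50% intervention.
- Pantry-only entrants, case A (no benefit): 20% insecure in both arms.
- Pantry-only entrants, case B (funds prevent worsening): 40% control, 20% intervention.
- Outcome compared as a yes/no status, two-sided alpha 0.05.

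**Step 3: formulas.** The rate in each arm is (1 − q) × HVS-positive rate + q × pantry-only rate. In case A the difference is therefore (1 − q) × 30 points. In case B it is (1 − q) × 30 + q × 20 points. With p̄ the mean of the two rates pC and pT, d their difference and n = 30, power is

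Φ{ [d − 1.96 √(2p̄(1 − p̄)/n)] / √([pC(1 − pC) + pT(1 − pT)]/n) }.

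At q = 0: 80% vs 50%, (0.30 − 1.96 × 0.1232)/0.1169 = 0.50, power 69%.
At q = 20%, case A: 68% vs 44%, (0.24 − 1.96 × 0.1282)/0.1244 = −0.09, power 46%.

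**Step 4: results.**

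| q | Case A: difference, power | Case A: n per arm for 80% power | Case B: difference, power | HVS-positive only: n per arm, power |
|---|---|---|---|---|
| 0 | 30 points, 69% | 39 | 30 points, 69% | 30, 69% |
| 10% | 27 points, 57% | 51 | 29 points, 64% | 27, 64% |
| 20% | 24 points, 46% | 66 | 28 points, 60% | 24, 59% |
| 30% | 21 points, 37% | 88 | 27 points, 56% | 21, 53% |

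With a smaller assumed effect (80% vs 60%), power in case A is 39% at q = 0 and 24% at q = 20%.

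**Step 5: what the last column shows.** Restricting to HVS-positive entrants beats analysing everyone in case A (59% vs 46% at q = 20%). In case B it gains nothing material, and it loses at q = 30% (53% vs 56%). Making that subgroup the main analysis is a trade-off that depends on an unknown.

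**The case against.** A reader might infer that entrants who screen secure cannot improve and so add nothing. The documents do not support that. Someone secure at entry can become insecure over 12 weeks, and funds that prevent this produce a real difference between arms (case B). The unnamed instrument may also be graded finely enough to leave room for improvement.

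A reader might infer that the comparison is the only evidence that the funds worked. It is the only quantitative between-arm check described. Section 11.0 also plans open-ended questions on how helpful the food assistance was, and the interviews in Section 5.2 ask intervention-arm participants about its impact. Neither gives a quantitative contrast with control, but both bear on the question.

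A reader might infer that the outcome will certainly be dichotomised, at a calculable loss of information. That rests on the word status alone. Section 11.0 lists t-tests as well as chi-square tests and assigns neither to food security. Standard efficiency figures for cutting a normally distributed score at a known point do not carry over to an unnamed scale, or to a two-item screener.

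Three further points stand. The health-record prescreen means that those approached were once documented as food insecure, so q could be near zero, although an undated earlier result does not show insecurity in the 30 days before entry. The eligibility script and survey were filed separately with the ethics submission, and may already collect these items from everyone. And this is a pilot with feasibility and acceptability as primary endpoints; no decision rule depends on this contrast. These points limit the weight of the concern. They do not remove the contradiction in Section 6.2 or the absence of baseline food security from the analysis plan.

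**Conclusion.** The contradiction between the two bullets is a matter of text and needs no assumption: they must be reconciled.

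The statistical part is conditional. If pantry-only entrants are admitted and get no benefit on the measure used, the between-arm difference shrinks by the factor 1 − q: from an assumed 30 points to 27, 24 or 21 for q of 10%, 20% or 30%. If the funds prevent worsening as in case B, it shrinks only to 29, 28 or 27. The documents give neither q nor the instrument, so these figures show a range and do not predict. They also do not show that the pilot would reach a wrong conclusion, since the outcome is exploratory and the trial is not powered for it.

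What remains is an inexpensive improvement: a pre-randomisation score for everyone and a graded, baseline-adjusted comparison would make this outcome easier to interpret whatever q turns out to be.

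**What to change.** 1. Reconcile the inclusion and exclusion bullets in Section 6.2 so that they give the same answer for all four combinations in the table above.
2. Ask the food-security items of every entrant before randomisation, including any who qualify by pantry visit, and record the entry route. The baseline survey already precedes randomisation and can carry them.
3. In Section 11.0, name the food-security measure, its scoring and its recall period. State that week-12 food security will be compared between arms on the graded item score, taking the baseline score into account (for example, a regression of the week-12 score on arm and baseline score), in all randomised participants as allocated, with a confidence interval.
4. Show change in status among those insecure at baseline as a supporting table, not as the main result.

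The cost is at most two extra questions, if they are not already asked, and one analysis sentence. If the measure is only the two-item screener, its summed score is coarse and the gain from grading will be limited. The baseline score should be collected prospectively, because it cannot be reliably recovered after randomisation.

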### 2.2 Relevant Preliminary Data

There are many sources of socioeconomic stress that disproportionately affect populations with disadvantage. Food insecurity occurs when there is lack of access at all times to enough food for an active, healthy life. In 2019, 35% of households living below the federal poverty level (FPL) experienced food insecurity, compared to 5% of households above 185% of FPL. Food insecurity is also significantly higher among racial/ethnic minority households, female-headed households, and households with children. Food insecurity is an important social determinant of health that is independently predictive of a range of chronic disease outcomes, influencing health behaviors related to chronic diseases (such as medication adherence, diet quality, eating behaviors, and substance use). As such, food insecurity's effects on health behaviors are most widely considered within specific chronic diseases that are diet-sensitive (such as diabetes, hypertension, and hyperlipidemia), or are transmitted through risky behaviors especially among vulnerable populations (such as people living with HIV). Beyond behaviors within specific chronic diseases, food insecurity has also been linked with tobacco smoking behavior. Food insecurity is known to increase the odds of current smoking, independent of poverty and other socioeconomic indicators, as well as mental health characteristics that increase likelihood of smoking.

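### Nothing in the plan stops two members of one household from enrolling and being allocated to opposite arms, so shared food funds could dilute the exploratory between-arm contrast

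*Combined protocol and SAP*

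**What the plan says.** **Eligibility.** Section 6.2 sets criteria for age, daily smoking, willingness to quit and food insecurity, plus "A reliable telephone number and a local mailing address where participant can be reached during the duration of the study". The exclusions mirror these. None mentions other members of the household.

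**Recruitment.** Sections 5.2 and 7.3 build a list of individual patients from the health records of 7 sites. "Using this list, we will send out a recruitment packet in the mail", and where telephone follow-up is needed, "we will randomly follow up with individuals on the list until we reach the enrollment target for the wave". Neither section describes a check for people living together.

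**Randomisation.** Section 1.0 states "We will recruit 60 participants for a 12-week study" and that "half of the participants (n=30) will be randomly assigned to the intervention arm". Section 5.2 says "participants will be randomized in the Intervention arm or the Control arm with a 50/50 chance to be randomized in either arm". The unit is the individual. No household unit or stratum is named.

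**Funds.** Section 5.2 gives the intervention arm $83 a month, $250 in total, "to partially support the cost of food". Payment is by gift card, check, deposit or electronic transfer, with no stated limit on how it is spent. Section 2.2 reports food insecurity by household ("35% of households living below the federal poverty level (FPL) experienced food insecurity") and describes tobacco costs as competing with household spending.

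**Use of the contrast.** Section 3.0 makes feasibility and acceptability the primary endpoints. Section 11.0 adds preliminary estimates of cessation and food security, and compares the arms by exploratory t-tests and chi-square tests.

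**The concern.** The two arms are meant to differ in one thing, the food funds. If a control participant lives with an intervention participant and some of that money reaches the shared kitchen, the control participant is partly treated and the intervention participant partly untreated. The observed difference in food security, and in cessation if it responds to food security, would then be smaller than the difference the intervention can produce.

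Section 1.0 states the main research question as whether addressing food insecurity during a quit attempt improves quitting, and says the findings will serve as the basis for later research. A diluted estimate would carry forward into that planning. With 30 per arm, each discordant pair is one thirtieth of each arm.

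**Working it through.** **Plan figures.** 60 participants, so 60/2 = 30 per arm, as Section 1.0 states. The documents give no alpha, power, effect size or standard deviation, so there is no sample-size calculation to reproduce. They also give no rate of same-household enrolment and no share of funds passed on.

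**Assumed inputs.** *m*, the number of enrolled same-household pairs: 1, 2, 3 or 5. *f*, the share of the funds that passes from the intervention member to the control member: 0.25 or 0.50. The two participation periods are taken to overlap fully.

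**Step 1: chance that a pair is discordant.** With a fixed 30/30 split, once one member is placed, 30 of the remaining 59 places are in the other arm: 30/59 = 50.8%. With simple 50/50 randomisation it is 50%.

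**Step 2: loss per discordant pair.** The intervention member loses *f* of the funds and the control member gains *f*. Each arm mean shifts by *f*/30 of the funds, in opposite directions, so the contrast falls by 2*f*/30.

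**Step 3: expected and worst-case dilution.** Expected = *m* × (30/59) × 2*f*/30 = 2*mf*/59. Worst case, with every pair discordant = 2*mf*/30.

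| Enrolled pairs *m* | Expected discordant pairs | Expected, *f* = 0.25 | Expected, *f* = 0.50 | Worst case, *f* = 0.50 |
|---|---|---|---|---|
| 1 | 0.51 | 0.8% | 1.7% | 3.3% |
| 2 | 1.02 | 1.7% | 3.4% | 6.7% |
| 3 | 1.53 | 2.5% | 5.1% | 10.0% |
| 5 | 2.54 | 4.2% | 8.5% | 16.7% |

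At *m* = 0 every entry is zero. These are losses in the *funds* contrast. They carry over to food security or cessation only if the effect is linear in the funds.

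**Step 4: what that would mean for sensitivity.** Assume a two-sided 5% test and a normal approximation. The standardised difference giving 80% power at 30 per arm is (1.960 + 0.842) × √(2/30) = 0.72. Shrinking it by 1.7%, 5.1%, 8.5% or 16.7% lowers power to 78.6%, 75.8%, 72.7% or 64.6%. The plan makes no power claim, so this is only a scale for the table.

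**Step 5: independence.** Let *C* and *D* be the numbers of concordant and discordant pairs, and ρ the correlation between members of a pair. The variance of a difference in means is 2σ²/30 + (2ρσ²/30²)(*C* − *D*), a relative change of ρ(*C* − *D*)/30. The expected value of *C* − *D* is *m*(29/59 − 30/59) = −*m*/59. For 5 pairs, even with ρ = 1, the expected relative change is 5/(59 × 30) = 0.3% in size. On average the two kinds of pair nearly cancel.

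**The case against.** The strongest case on the other side has four parts.

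**Sharing is not documented.** A reader might infer from the household statistics in Section 2.2 that the funds *are* shared. The documents do not say so. Section 5.2 describes the aid as serving the participant's own food needs, and the household evidence is background. This stands: sharing is a reasonable inference, no more. Equally, a statement of intent does not prevent unrestricted money from entering a common budget.

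**Pairs may never occur.** Both members must be listed patients, smoke daily, meet the food-insecurity criterion, be willing to quit within 30 days and agree to join, and only 60 people are taken from 7 sites. This also stands: the number may be zero.

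**Little rests on the contrast.** The primary endpoints are feasibility and acceptability, and the tests are exploratory. This limits the importance of the point but does not remove it, because Section 11.0 sets out to derive preliminary cessation and food-security estimates.

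**The eligibility script is not in the documents.** Section 5.3 says it is attached to the ethics submission, so a household question there can be neither confirmed nor excluded. If it exists, the rule still belongs in Section 6.2.

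The privacy request in Section 5.3 does not answer the point. It is aimed at theft of gift cards and does not keep apart two people who each receive a packet at the same address.

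**Conclusion.** The omission is real: eligibility, recruitment and individual randomisation all leave co-residents free to enrol and to be split between arms. The consequence is conditional and modest. The expected dilution of the funds contrast is about 0.8% to 8.5%, assuming 1 to 5 enrolled pairs, 25% to 50% of funds passed on and overlapping participation.

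Two stronger readings are not supported. One is that a loss near 17% should be expected. That needs 5 discordant pairs with equal sharing. Since about half of pairs are discordant, 5 would typically require about 10 enrolled pairs (5 ÷ 30/59 = 9.8), or 20 of the 60 participants, and nothing in the documents suggests this. The other is that household pairs invalidate the t-tests and chi-square tests. With a few pairs, the effects of concordant and discordant pairs on the variance nearly cancel in expectation.

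The point is a cheap improvement.

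**What to change.** Add one exclusion to Section 6.2: *Another member of the household is or has been enrolled in this study.* The words *has been* cover the 3 to 4 successive enrolment waves. Ask it as a direct question at the screening call, with the mailing address used only as a prompt. People should not be deleted from the health-record list on a duplicate address alone, because unrelated people can share an address and would be lost before anyone spoke to them.

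The target of 60 is unchanged, and discordant pairs fall to zero to the extent that answers are accurate. The cost is one eligibility line, one screening question and a few otherwise eligible people turned away. If the sponsor prefers to turn no one away, the alternative is to allocate co-residents to the same arm, record household membership at baseline and allow for the clustering in the analysis. That is more work for a trial of this size.
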